The Safety and Efficacy of the Transnasal Humidified Rapid-Insufflation Ventilatory Exchange (THRIVE) for Short Diagnostic Bronchoscopy Procedures

Study Protocol
NCT03086408

February 21, 2017

STUDY OBJECTIVES

1. DETERMINING THE SAFETY AND EFFICACY OF THRIVE FOR SHORT DIAGNOSTIC BRONCHOSCOPIC PROCEDURES.

THRIVE should improve glottic and tracheal exposure, operating conditions, decrease surgical time, and potentially lead to better patient outcomes. The safety of THRIVE for short diagnostic bronchoscopy has not been formally investigated, and will be explored in this study. With the patient anesthetized, apneic, and adequately oxygenated with THRIVE, the build-up of carbon dioxide in patient's blood (PaCO₂) and ensuing acute hypercapnic acidosis will be the main factors limiting the duration of THRIVE administration. At present, the rate of PaCO₂ rise with THRIVE has not been directly investigated, but is suggested to be 1.1 mm Hg per minute. It is expected that the short duration of diagnostic bronchoscopy procedures explored in this study will not lead to substantial rise of PaCO₂. The PaCO₂ rise to 70 mm Hg is considered a safe level for moderate hypercapnia in patients without significant comorbidities (see Exclusion Criteria).

2. DETERMINING POSSIBLE BENEFICIAL EFFECT OF THRIVE ON IMMEDIATE POSTOPERATIVE RECOVERY, OPIOD CONSUMPTION, AND FUNCTIONAL RECOVERY.

INCLUSION CRITERIA

Subjects presenting for short diagnostic bronchoscopy procedures under general anesthesia, including patients after bone marrow transplant (BMT).

EXCLUSION CRITERIA

1. Patients with significantly decreased myocardial function.
2. Patients with cardiac arrhythmias.
3. Patients with significant peripheral vascular disease.

STUDY PROTOCOL: THRIVE AND DIAGNOSTIC BRONCHOSCOPY

2

4. Patients with known significant cerebrovascular disease.
5. Patients with significant renal insufficiency.
6. Patients with electrolyte (K+, Ca++) abnormalities.
7. Patients with increased intracranial pressure or reduced intracranial compliance.
8. Patients with skull base defects.
9. Patients with pulmonary hypertension.
10. Immunocompromised patients.
11. Patients with significant chronic lung diseases.
12. Morbidly obese patients.
13. Patients with severe and poorly controlled gastsroesophageal reflux disease.
14. Patients with hiatal hernia and full stomach patients.
15. Patient's refusal to participate in the study.
16. Patients who do not understand English or mentally handicapped.
17. Pregnant or breastfeeding patients.
18. "BMT patients with SpO2 < 90% on supplemental nasal oxygen up to 6 l/min, or those requiring non-rebreather mask to keep SpO2 > 90% will be excluded from the study."

PROTOCOL AT A GLANCE AND STUDY END-POINTS

1. Patients will be randomly assigned to either THRIVE or ETT/SGA (control group).
2. Anesthetic management is standardized for both groups.
3. Study end-points: per data collection sheet.

OPERATING ROOM PREPARATION

1. All drugs, airway supplies, eye tape, per routine.
2. 8.0 MLT ETT and SGA (i-Gel).
3. Precut large Tegaderm for securing ETT to the chin in left corner of mouth.
4. Four channel Alaris pump with:
 - a. NS carrier at 50 ml/hr
 - b. Propofol drip
 - c. Remifentanil drip
5. 20 ml NS syringe in line for chasing the induction and IVP drugs intraop. Please minimize IVF beyond 10 ml/kg total due to high incidence of urinary retention in male patients.
6. Working PNS with pads (make sure the battery is fresh).
7. Sedline or BIS.

STUDY PROTOCOL: THRIVE AND DIAGNOSTIC BRONCHOSCOPY

	THRIVE GROUP	CONTROL GROUP
PREOP and PREMEDICATION	
 • Obtain (check for) patient's consent. • Randomize the patient to either THRIVE or CONTROL group. • Obtain preop QoR15. • Peripheral IV, 20 g. • Midazolam 0.007 mg/kg incremental doses to achieve sufficient anxiolysis, not to exceed 0.025 mg/kg total dose. For elderly patients (70-80 y.o), limit total dose of Midazolam to 0.5 mg. 	
PRE-INDUCTION:	
Place standard ASA monitors, Sedline (BIS), and peripheral nerve stimulator (TOF ulnar nerve)
 
 • Apply THRIVE (FiO₂ 1.0) at 30 l/min. • Make sure the patient's head is elevated 30-40° (table in BACK UP position, not reverse Trendelenburg). 	
Preoxygenate.
 
 • IV fluid loading completed: 5 ml/kg. • IV Glycopyrrolate 0.2 mg if HR ≤ 50 bpm for elderly patients (70-80 y.o.). • Assure all bronchoscopy supplies are ready for immediate use in THRIVE group. • Both anesthesia and surgical time-outs completed.
INDUCTION	
 • IV Remifentanil 1 mcg/kg, Propofol 2mg/kg IV, Rocuronium 0. 6mg/kg IV. • Additional Remifentanil 0.5 mcg/kg and/or Propofol 0.5 mg/kg IV boluses, as required per hemodynamic responses and Sedline/BIS readings. 	
	
 • Turn THRIVE to 70 l/min. • Maintain jaw thrust, with oral airway as necessary, throughout the procedure. 	
 • Mask ventilation as required. • Place SGA or ETT.
MAINTENANCE	
 • TIVA + THRIVE (FiO₂ 1.0) at 70 l/min. • NBP q 5 min, unless indicated more frequently. 	
 • TIVA + O₂:Air; FiO₂ = 0.5 or higher as required • NBP q 5 min, unless indicated more frequently.

STUDY PROTOCOL: THRIVE AND DIAGNOSTIC BRONCHOSCOPY

5

	
• If $\text{SpO}_2 < 90\%$, or ventricular arrhythmias, discuss with surgeon converting to either SGA or ETT.• If surgical duration more than 30 min, consider converting to either SGA or ETT. 
• Mechanical ventilation to normocapnia: EtCO_2 35-40 mmHg.• $\text{Vt} 6-8 \text{ ml/kg}$ of predicted body weight (PBW), PEEP 5 cmH₂O.• PBW Males = $50 + 2.3 (\text{Height}'' - 60)$• PBW Females = $45.5 + 2.3 (\text{Height}'' - 60)$
MAINTENANCE (cont.)	
• Sedline/BIS-guided TIVA with Propofol/Remifentanil to maintain PSI 25-50 (BIS 40-60).• Maintain main IV at TKO. All IV bolus drugs are chased by 15 ml of NS using in-line 20 ml syringe.• TIVA dosing:
○ TIVA is carried in by Alaris NS carrier at 50 ml/hr.○ For normal weight patients, dose Prop/Remi infusions per total body weight.○ For obese patients ($\text{BMI} \geq 30$), dose Prop/Remi infusions per lean body weight (LBW). Simplified LBW formula: $\text{LBW} = \text{IBW} \times 1.2$; $\text{IBW} = 22 \times \text{Ht(m)}^2$.○ Propofol 80-150 mcg/kg/min, Remifentanil 0.05-0.3 mcg/kg/min. Optimize Remifentanil dose first.○ Rocuronium boluses 0.15 mg/kg, to maintain 0-1/4 TOF at ulnar nerve.• Treating hypertensive responses (MAP > 20 mmHg from baseline):
○ Remifentanil 0.5 mcg/kg and Propofol 0.5 mg/kg boluses q 2 min, as required per hemodynamic responses and Sedline/BIS readings○ Labetalol 0.07 mg/kg boluses q 10 min up to a total dose of 1 mg/kg, as required per hemodynamic responses and Sedline/BIS readings○ Fentanyl 0.5 mcg/kg IV bolus, total dose limit 1 mcg/kg, only if perceived need for additional analgesia after Remifentanil had been maxed out at 0.3 mcg/kg• Treating hypotensive responses (MAP < 20 mmHg from baseline):
○ Crystalloid loading 5 ml/kg x 1○ Ephedrine 5 mg IV if HR < 60 bpm, or Phenylephrine 100 mcg IV if HR > 60 bpm

STUDY PROTOCOL: THRIVE AND DIAGNOSTIC BRONCHOSCOPY

6

	
○ Vasopressin 1 unit IVP prn, as required○ Phenylephrine drip, as required, start at 0.3 mcg/kg/min, increase in 50% increments
EMERGENCE	
• Zofran 4 mg IV.• Reverse NMB with Sugammadex, as following: 2 mg/kg for TOF 1-2/4; 4 mg/kg for TOF 0/4, with posttetanic count of 1-2.• Discontinue TIVA and disconnect TIVA line upon completion of surgery.• Transport to PACU: FMO₂ at 6 l/min. 
• Maintain THRIVE at 70 l/min with jaw thrust ± oral airway as required, until return of spontaneous ventilation and consciousness.• Extubate per routine.
STANDARDIZED POSTOP ORDERS	
• IV Fentanyl 25 mcg boluses q 5 min prn VAS ≥ 4, total dose 250 mcg.• PO Hydrocodone-acetaminophen (NORCO) 5-325 mg, 1 tab prn VAS ≥ 4, may repeat x 1.• If allergic to NORCO, Oxycodone-acetaminophen (PERCOCET) 5-325 mg, 1 tab prn VAS ≥ 4, may repeat x 1.• IV Demerol 10 mg for shivering only, may repeat x 1.• Treatment of PONV:
○ Zofran 8 mg IV x 1○ If no effect, and no contraindications, add IV Promethazine 12.5 mg x 1
PACU DATA COLLECTION	
• Obtain PACU data collection sheet and QoR15.
QUESTIONNAIRES and DIARIES	
• Pre- and post-procedural QoR15 questionnaires and post-procedural home diaries will be given to the patients. The BMT patients will receive QoR15 questionnaires, but will not keep the home diaries.

STUDY PROTOCOL: THRIVE AND DIAGNOSTIC BRONCHOSCOPY

7

THRIVE PROTOCOL	
PREOP	
• Randomize patient to THRIVE or ETT group.
PREINDUCTION	
• Start THRIVE @ 30 l/min immediately, before applying other OR monitors.• Maintain patient's head elevated 30-40°, with table in BACK UP, not reverse Trendelenburg position.
INDUCTION	
• THRIVE @ 70 l/min.• Place an oral intubating airway and maintain a jaw thrust for introduction of the fiberoptic scope by surgeon.
MAINTENANCE	
• Maintain THRIVE @ 70 l/min.• Maintain jaw thrust with the intubating oral airway in place for the duration of the procedure.• If surgery prolonged (over 30 min), consider converting to either SGA or ETT.
EMERGENCE	
• Maintain THRIVE at 70 l/min with jaw thrust ± oral airway as required, until return of spontaneous ventilation and consciousness.

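### BMT status has its own entry rule and diary schedule, but neither the stated randomisation nor the SAP's analysis uses it, which costs precision and leaves a small trial exposed to chance imbalance

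*Protocol*

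**What the plan says.** **Who enters.** The protocol's Inclusion Criteria admit "Subjects presenting for short diagnostic bronchoscopy procedures under general anesthesia, including patients after bone marrow transplant (BMT"). Exclusion 18 is an oxygenation rule written for this group alone. It removes "BMT patients with SpO2 < 90% on supplemental nasal oxygen up to 6 l/min, or those requiring non-rebreather mask to keep SpO2 > 90"%. Exclusion 10 reads "Immunocompromised patients", with no stated exception for BMT.

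**What is measured.** Under Questionnaires and Diaries: "The BMT patients will receive QoR15 questionnaires, but will not keep the home diaries". QoR15 is therefore collected in everyone and the home diary only in non-BMT patients. For the remaining endpoints the protocol says "Study end-points: per data collection sheet"; that sheet is not reproduced.

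**How patients are allocated.** Protocol at a Glance, item 1: "Patients will be randomly assigned to either THRIVE or ETT/SGA (control group"). The preoperative step of the management table says "Randomize the patient to either THRIVE or CONTROL group", and the THRIVE summary table repeats the step without further detail. No ratio, block size or stratification factor is given.

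**How arms are compared.** The SAP is one paragraph: unpaired t-tests with 95% confidence intervals, and a chi-square test for gender. It has no BMT covariate, stratum or subgroup. Its wording covers patient characteristics, and it names no separate method for outcomes.

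**The concern.** The protocol treats BMT patients as a distinct group at entry and in data collection, then makes no stated use of that distinction in allocation or analysis. BMT status is one binary factor, known before randomisation.

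It could plausibly be prognostic. Exclusion 18 suggests that baseline oxygenation was a particular concern in these patients, and the protocol's prompt to discuss conversion is an SpO2 below 90%. The documents do not quantify the link.

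Three things are at stake:
- Precision: between-group variation that a model could remove stays in the error term.
- Interpretability of the one allocation obtained: a chance imbalance would leave an unadjusted difference hard to read.
- Reporting: the 70 mm Hg PaCO₂ premise is "considered a safe level for moderate hypercapnia in patients without significant comorbidities (see Exclusion Criteria"). A pooled result cannot show how the technique was tolerated in each group, however well the arms balance.

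**Working it through.** The plan gives no sample size, power, standard deviation, allocation ratio or BMT share, so it has no figure to reproduce. Everything below rests on assumed inputs, shown as ranges.

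**1. Chance of imbalance.** Assume equal arms of n = N/2 and K BMT patients in total. Under unstratified allocation, the number x of BMT patients in one arm is hypergeometric (N, K, n). The share difference is |x − (K − x)|/n = |2x − K|/n.

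Example: N=40, 10% BMT, so K=4 and n=20. A difference of at least 0.20 needs |2x − 4| ≥ 4, so x = 0 or 4. The probability is 2 × C(20,4)/C(40,4) = 2 × 4,845/91,390 = 0.106.

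Probability of a difference of 20 points or more:

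| N | 10% BMT | 25% BMT | 50% BMT |
|---|---|---|---|
| 40 | 10.6% | 27.3% | 34.3% |
| 60 | 2.4% | 7.2% | 19.6% |
| 80 | 0.5% | 6.9% | 11.7% |
| 100 | 0.1% | 2% | 7% |

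If the BMT count is itself left random (independent binomial counts per arm), the N=40 figures become 6%, 20% and 27%. At N=200 none exceeds 0.6%.

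**2. What an imbalance does.** The shift in the unadjusted arm difference is imbalance × BMT effect. At 20 points this is 0.20 × 0.5 SD = 0.10 SD, or 0.20 × 1 SD = 0.20 SD. Here SD is the within-group standard deviation.

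**3. Type I error.** Simulation with 20,000 null trials per setting, N = 40, 60 and 100, BMT share 25% or 50%, BMT effect 0.5 or 1 SD, two-sided 5% tests:

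| Design and analysis | Type I error |
|---|---|
| Unstratified, t-test, all trials | 0.048–0.052 |
| Same, only trials with ≥20 points imbalance, effect 0.5 SD | 0.06–0.085 |
| Same, effect 1 SD | 0.08–0.17 |
| Those imbalanced trials, adjusted for BMT | 0.044–0.061 |
| Stratified, t-test, effect 1 SD | 0.030–0.035 |
| Stratified, adjusted for BMT | 0.048–0.053 |

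**4. Precision.** With BMT share p and effect g (in SD), the variance facing the t-test is 1 + g²p(1 − p). At g = 1 and p = 0.5 it is 1 + 0.25 = 1.25, so adjustment removes 0.25/1.25 = 20% of it. At g = 0.5 and p = 0.5 it is 1.0625, and adjustment removes 0.0625/1.0625 = 6%.

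Simulated power for a true arm effect of 0.8 SD, with p = 0.5 and g = 1:

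| N | Unstratified, t-test | Unstratified, adjusted | Stratified, t-test | Stratified, adjusted |
|---|---|---|---|---|
| 40 | 0.600 | 0.681 | 0.599 | 0.687 |
| 60 | 0.777 | 0.860 | 0.807 | 0.865 |

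Most of the gain comes from adjustment. With g = 0.5 it is small: 0.667 to 0.691 at N=40.

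**The case against.** The strongest reply is that randomisation without strata is valid. The t-test already allows for chance imbalance, and overall type I error stays at 0.05. That stands. A reader might infer that the missing stratification biases the trial or drives its result. The documents do not support this: error rises only among trials that happen to be badly imbalanced, and only if BMT status is strongly prognostic.

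Other limits also stand:
- **Silence is not evidence.** The documents do not describe the randomisation method. One may say that stratification is not stated, but not that the pool was unstratified.
- **The BMT share may be small.** Exclusion 10 carries no BMT exception, and at 10% BMT the risk falls to 2.4% at N=60.
- **Diary outcomes cannot be confounded by BMT mix**, because only non-BMT patients keep diaries. What remains is a narrower population and possibly unequal diary numbers by arm.
- **Conversion to SGA or ETT is described only for the THRIVE arm.** Controls already have one of these devices, so there is no arm comparison to distort.
- **Exclusion 18 restricts BMT entry.** It should not be read as a rule that relaxes entry for sicker patients; exclusions 1–14 state no BMT exemption.

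The reply does not answer the loss of precision, the lack of results by BMT status, or the unstated limit on diary conclusions.

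**Conclusion.** The point holds as one of precision, conditional protection and reporting, not of bias. The documents establish that BMT status is used at entry and in data collection, and that no use of it is stated in allocation or analysis.

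The size is conditional on N, BMT share and BMT effect, none of which the documents give. If N is about 40 and BMT patients are a quarter to a half of the sample, an imbalance of 20 points or more is a realistic prospect (27–34%). By N=100 it is 7% or less. With a 1 SD effect and half the patients BMT, leaving BMT status out of the model costs about 8 percentage points of power (0.600 against 0.681 at N=40; 0.777 against 0.860 at N=60). With a weak effect or a small share, little is lost.

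This also assumes that the SAP's t-test is meant for outcomes as well as for the patient characteristics it names. Limiting diary conclusions to non-BMT patients and reconciling exclusion 10 with the inclusion criterion depend on none of these assumptions.

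**What to change.** 1. State the randomisation method, and randomise in permuted blocks stratified by BMT status (yes/no).
2. For outcome comparisons such as QoR15, replace the unadjusted t-test with a linear model containing arm and BMT status. Stratifying while keeping the t-test would be conservative. If allocation is already complete, as the SAP's past tense and its 2020 date suggest it may be, make this adjustment alone and label it as added later.
3. Report oxygenation and QoR15 by arm within BMT strata, and conversion within the THRIVE arm by BMT status.
4. State that home-diary (functional recovery) conclusions apply to non-BMT patients only.
5. Separately, reconcile exclusion 10 with the inclusion of BMT patients, so that the eligible population is unambiguous.

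Cost: a second randomisation list, one covariate (one degree of freedom) and one extra table. A small stratum may end with an incomplete block, and its within-stratum results would be descriptive only.

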The Safety and Efficacy of the Transnasal Humidified Rapid-Insufflation Ventilatory Exchange (THRIVE) for Short Diagnostic Bronchoscopy Procedures

Statistical Analysis Plan

NCT03086408

June 9, 2020

Means and standard deviations were calculated for each of the patient characteristics. The statistical significance of differences between THRIVE and non-THRIVE patients was assessed using unpaired two sample Student's t-test with 95% confidence interval for all patient characteristics, without adjusting for multiple comparisons. For patients' gender, a chi-square test was used.

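### QoR15 is taken before the procedure and again in PACU, but the SAP gives the baseline score no role; adjusting the PACU score for it could add precision at almost no cost.

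*Protocol*

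**What the plan says.** In the protocol's main table, the preoperative row for both arms reads "Randomize the patient to either THRIVE or CONTROL group. • Obtain preop QoR15". The PACU row reads "Obtain PACU data collection sheet and QoR15". The questionnaires row confirms the pair: "Pre- and post-procedural QoR15 questionnaires and post-procedural home diaries will be given to the patients". It exempts transplant patients from the diaries only: "The BMT patients will receive QoR15 questionnaires, but will not keep the home diaries". A before-and-after QoR15 pair is thus planned for every patient.

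Objective 2 begins "DETERMINING POSSIBLE BENEFICIAL EFFECT OF THRIVE ON IMMEDIATE POSTOPERATIVE RECOVERY" but does not name QoR15 as its measure. The end-points are given by reference: "Study end-points: per data collection sheet".

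The SAP is one paragraph. It gives means and SDs, an "unpaired two sample Student's t-test with 95% confidence interval for all patient characteristics, without adjusting for multiple comparisons", and a chi-square test for gender. It mentions neither QoR15 nor any covariate, change score or adjusted model.

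**The concern.** QoR15 is the only questionnaire the protocol lists both before and after the procedure, and the second objective concerns immediate recovery. The usual reason to take a baseline on the same scale is to remove between-patient variation from the later comparison. Nothing in the SAP does this. If preoperative QoR15 counts as a patient characteristic, its only use would be a between-group test of a pre-treatment score, which adds nothing to the precision of the recovery comparison.

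What is at stake is the width of a confidence interval. If preoperative and PACU scores are at least moderately correlated, a score already collected would narrow the interval without another patient. If they are weakly correlated and the trial is small, there is nothing to gain.

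**Working it through.** **Inputs.** The documents supply the two measurement times, random assignment to two groups and the 95% confidence level. They do not supply the sample size, allocation ratio, SD or correlation between preoperative and PACU QoR15 (ρ). There is no plan figure to reproduce. Assumed here: equal arms, normally distributed scores, a common ρ in both arms of 0, 0.3, 0.5 or 0.7, and a total N of 20, 40 or 100.

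**Variance.** In large samples, the variance of the treatment difference from ANCOVA divided by the unadjusted variance is 1 − ρ²: 0.91, 0.75 and 0.51 for ρ = 0.3, 0.5 and 0.7, so the variance falls by 9%, 25% and 49%. In small samples the slope must be estimated, and the ratio becomes

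(1 − ρ²) × (1 + 1/(N − 4)).

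For example, N = 20 and ρ = 0.5 give 0.75 × (1 + 1/16) = 0.797, a 20% cut.

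**Interval width.** ANCOVA also spends one degree of freedom, so the approximate width ratio is √(variance ratio) × t(N − 3)/t(N − 2), using 97.5% quantiles. For N = 20 and ρ = 0 this is √1.0625 × (2.110/2.101) = 1.035.

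**Break-even.** Setting the variance ratio to 1 gives ρ² = 1/(N − 3). At N = 20 this is √(1/17) = 0.243.

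| Total N | Variance ratio, ρ = 0 / 0.3 / 0.5 / 0.7 | CI width ratio, ρ = 0 / 0.3 / 0.5 / 0.7 | Break-even ρ (variance) |
|---|---|---|---|
| 20 | 1.063 / 0.967 / 0.797 / 0.542 | 1.035 / 0.987 / 0.896 / 0.739 | 0.24 |
| 40 | 1.028 / 0.935 / 0.771 / 0.524 | 1.015 / 0.968 / 0.879 / 0.725 | 0.16 |
| 100 | 1.010 / 0.919 / 0.758 / 0.515 | 1.005 / 0.959 / 0.871 / 0.718 | 0.10 |

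**Check.** Simulation with 10,000 trials per cell gave variance ratios of 1.062, 0.971, 0.800 and 0.555 at N = 20 and 1.028, 0.937, 0.761 and 0.532 at N = 40, for ρ = 0, 0.3, 0.5 and 0.7. All lie within 0.015 of the formula.

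**Why not a change score.** With equal pre and post SDs, its variance ratio against the unadjusted comparison is 2(1 − ρ): 1.40, 1.00 and 0.60 for ρ = 0.3, 0.5 and 0.7. It is worse than no adjustment below ρ = 0.5, and in large samples it is worse than ANCOVA at each of these values.

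**The case against.** Four objections have weight.

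- *There is no analysis to adjust.* The SAP specifies no comparison of PACU QoR15. This stands, and it makes the point an add-on to a larger gap. But the covariate is best chosen when that outcome analysis is written; otherwise the SAP's only method for means, an unadjusted t-test, is the likely default.
- *QoR15's role as an end-point is inferred.* The end-points are referred to a data collection sheet that is not among the documents, and the PACU row names QoR15 beside a sheet, not clearly as part of one. This stands. The claim is only that the SAP gives the baseline score no use; what the sheet says is unknown.
- *This is a general argument for ANCOVA, with no figure from this trial behind it.* The gain indeed cannot be sized. The trial-specific part is that the baseline is already planned for every patient, so the downside is small and bounded.
- *It may be too late.* The SAP is dated June 9, 2020 and written in the past tense. If the data had been seen, the ANCOVA is a post hoc second estimate. This limits its standing and must be stated with the result.

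A reader might go further and infer that the baseline is contaminated, because the preoperative row lists QoR15 after randomisation. The documents do not support this. They do not say when the patient learns the allocation, and in the main table the arms first differ at pre-induction, a later row. Order within the tables is also weak evidence of order in time: the main table's pre-induction row names the monitors ahead of THRIVE, while the separate THRIVE page says "Start THRIVE @ 30 l/min immediately, before applying other OR monitors", a difference for the protocol's authors to reconcile. No such bias is shown.

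**Conclusion.** The point holds as a free improvement. The SAP leaves a planned baseline QoR15 score without a role, and ANCOVA would use it. Over the assumed correlations of 0.3 to 0.7, the confidence interval would be about 1% to 26% narrower at 20 patients and 4% to 28% narrower at 100. The worst case, no correlation, is an interval about 3.5%, 1.5% or 0.5% wider at 20, 40 or 100 patients. Below the break-even correlations there is no gain in variance. All these figures rest on assumed correlations and sample sizes, equal arms and normal scores.

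A reader might also infer that an unadjusted comparison would be invalid or biased. It would not be: randomisation makes the unadjusted difference in PACU QoR15 unbiased, and it does not use the baseline score at all. Nor do the documents say that QoR15 is the measure of the second objective.

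**What to change.** When the outcome analysis is written, add to the SAP:

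> PACU QoR15 will be compared between the groups as randomised by ANCOVA with preop QoR15 as the only covariate, giving the adjusted mean difference with 95% CI; the unadjusted difference with 95% CI will be shown beside it.

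Two conditions go with it. If the ANCOVA was added after the data were seen, label it post hoc. If preoperative QoR15 was taken after the patient knew the allocation, keep the unadjusted difference as the main estimate and make the ANCOVA the sensitivity analysis.

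The cost is one sentence and one extra estimate, plus a check of when the score was taken relative to disclosure of the allocation. No new patient data are needed.

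### The preop QoR15 is listed after randomisation with no masking described, so the preop score is open to influence from knowledge of the arm; reordering two steps removes this at no cost

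*Protocol*

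**What the plan says.** The PREOP and PREMEDICATION row of the protocol's main table is a single list that serves both arms. It opens with "Obtain (check for) patient's consent" and continues "Randomize the patient to either THRIVE or CONTROL group. • Obtain preop QoR15". Venous access and then midazolam follow.

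The separate THRIVE PROTOCOL page has one PREOP entry, "Randomize patient to THRIVE or ETT group", and does not mention QoR15.

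After the procedure, the PACU DATA COLLECTION row says "Obtain PACU data collection sheet and QoR15". The QUESTIONNAIRES and DIARIES row confirms that QoR15 is given before and after the procedure. Bone marrow transplant patients also receive it, but they keep no home diary.

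Study Objective 2 reads "DETERMINING POSSIBLE BENEFICIAL EFFECT OF THRIVE ON IMMEDIATE POSTOPERATIVE RECOVERY, OPIOD CONSUMPTION, AND FUNCTIONAL RECOVERY". It names no instrument, and the protocol defers the end-points to a data collection sheet that is not part of the text. The SAP describes unpaired t-tests and, for gender, a chi-square test, all on patient characteristics. It does not mention QoR15, change from baseline or baseline adjustment.

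**The concern.** A baseline is useful because it cannot have been affected by the allocation. A self-reported score taken after allocation loses that guarantee unless the arm is hidden from the patient and from the person handing over the form. A patient who has just heard that they will have the new technique, or the standard airway, may answer differently about how they feel.

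If that happens, and the preop score is then used as a baseline, the shift passes into the estimated THRIVE effect on recovery. It also weakens the preop score as a check that the arms were comparable before assignment. For bone marrow transplant patients, QoR15 is the only patient-completed recovery instrument that the protocol names.

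**Working it through.** The plan states no figure on this point, and the documents give no QoR15 mean, SD, effect size or sample size. The check is therefore a reading of the order of steps, followed by algebra.

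**Order of steps.**
1. Main table, both arms: consent, randomisation, preop QoR15, venous access, midazolam. The bullets are not numbered, but consent comes first and venous access comes before an intravenous drug, so the list reads as a time sequence.
2. THRIVE PROTOCOL page: randomisation is the only PREOP step. Nothing there moves QoR15 ahead of it.
3. No other section of either document places QoR15 before allocation.

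**Protection of the score.**
1. Neither document mentions masking of patients, staff or assessors, or a rule that withholds the arm until the form is complete.
2. The THRIVE PROTOCOL page says "Start THRIVE @ 30 l/min immediately, before applying other OR monitors". This comes before induction, and the control arm is simply preoxygenated with no sham described. An awake patient could therefore tell the arm by then. In the printed order this step comes after QoR15, so it does not show that the arm was known when the form was filled in.

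**Effect on a comparison.** Let θ be the true THRIVE-minus-control difference in the mean post-procedure score. Randomisation makes the expected true preop difference zero. Suppose knowledge of the arm shifts the preop score alone, so that the expected observed preop difference is d (THRIVE minus control). Let β be the slope of post on pre.

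- Change score: expected difference = θ - d, so the bias is -d.
- Baseline-adjusted: expected difference ≈ θ - β x d, so the bias is about -(β x d).
- Post-procedure scores alone: expected difference = θ, so the bias from this source is 0.

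If a higher score means better recovery (the documents do not state the direction), a preop score raised in the THRIVE arm understates its benefit and a lowered one overstates it.

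**If the post score moves too.** Let knowing the arm also shift the reported post score by e between arms. The three biases become e - d, e - β x d and e. When e = d, the change score cancels the shift. The result -d therefore holds only for a shift confined to the preop score.

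Neither d, e nor β can be obtained from the documents, so no value in points is given.

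**The case against.** The strongest reply is that randomising a patient is not the same as telling the patient the result. Nothing says that the arm is disclosed in the preop area. The first arm-specific step that a patient could notice is the start of THRIVE before induction, which the printed order places after both QoR15 and midazolam. If allocation stays with the anaesthesia team until then, and that team does not administer the form, the preop score is unaffected. This stands as a limit: the documents show exposure to bias, not bias. It does not make the order safe, because no passage requires the arm to be withheld.

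A reader might infer that the trial is open-label. The documents never say so; they are silent on masking.

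A reader might also infer that Objective 2 rests on QoR15 before versus after the procedure. The objective does not name QoR15, PACU data and home diaries are collected as well, and the SAP sets out no QoR15 analysis. The preop score may never enter an effect estimate.

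Finally, a reader might expect baseline forms to be missing unevenly by arm. Nothing in the documents suggests that patients decline the form after learning their arm.

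**Conclusion.** The point holds as a procedural weakness of modest weight. As written, the order of steps leaves the preop score of a patient-reported recovery questionnaire open to knowledge of the arm, and neither document closes that opening.

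A bias in the result needs two further conditions, neither of which the documents confirm or exclude: the patient or the administrator learns the arm before the form is complete, and the preop score is used in the analysis. If both hold and only the preop score shifts, the bias is -d for a change score and about -(slope x d) after baseline adjustment. It is zero for a comparison of post-procedure scores alone. The size cannot be estimated from the documents.

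The stronger statement, that the baseline is in fact distorted and the recovery result biased, is not supported.

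**What to change.** In the PREOP and PREMEDICATION row, move the preop QoR15 step to after the consent check and before randomisation, so that the score is complete before the arm exists. The form, staff and visit stay the same, so the change costs nothing beyond reordering two adjacent bullets. The THRIVE PROTOCOL page does not mention QoR15 and needs no matching edit.

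The change protects the preop score only. Any effect of knowing the arm on the post-procedure QoR15 (e above) remains, whichever comparison is used.

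The SAP is dated June 2020 and written in the past tense, so enrolment may already be over. In that case the sponsor can instead report when the preop QoR15 was completed relative to allocation and disclosure, and whether and how that score enters the analysis.
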